8.1.4 Analysis of continuous longitudinal data

Changes from baseline at specified follow-up assessment time points will be analyzed using a mixed model for repeated measures (MMRM) under the MAR framework. Analyses will include the fixed, categorical visit (including baseline). An unstructured (co)variance structure will be used to model the within-participant errors. If this analysis fails to converge, the following structures will be tested: a heterogeneous Toeplitz covariance structure followed by the heterogeneous first-order autoregressive covariance structure will be considered. The covariance structure converging to the best fit, as determined by Akaike's information criterion, will be used as the primary analysis. The Kenward-Roger approximation will be used to estimate de-nominator degrees of freedom. Mean changes from baseline will be assessed using appropriate contrasts of least-squares means. Two-sided 95% confidence intervals will be provided.

8.2 STATISTICAL ANALYSES

All analyses will be at least provided overall and by histological status (UC with variant; UC without variant). For some effectiveness endpoints, additional subgroup analyses will be specified hereafter.

8.2.1 Primary criterion analyses

The primary criterion is the Overall Survival, evaluated in the FAS.

This criterion will be analyzed using the Kaplan-Meier method and survival curves will be presented. The starting date to be used is the date of first intake of study treatment.

The censoring and event date options to be considered for the OS analysis are defined as follows:

PFIZER CONFIDENTIAL

CT24-WI-GL03-RF02 2.0 *Non-Interventional Statistical Analysis Plan For Primary Data Collection Study*

01-Jun-2020

Page 17 of 28

Table 1: Event Date and Outcome for Overall Survival

Scenario	Date of Event/Censoring	Outcome
Death during study	Date of death	Event
Death after treatment discontinuation	Date of death	Event
Alive	Date of last contact	Censored
Lost to follow-up	Date of last contact	Censored

OS will also be described by subgroup (See section 5.3 for subgroup definition).

8.2.2 Secondary criteria analyses

8.2.2.1 Overall survival 2

For OS since chemotherapy initiation, endpoint will be analyzed using survival analysis method, using the same censorship as for primary criterion (Table 1), in the FAS. The starting date to be used is the date of first intake of chemotherapy as reported in the medical history. To avoid any immortal time bias between first intake of chemotherapy and the start of study treatment (avelumab), a modified Kaplan-Meier estimator will be provided using right censoring and left truncation, stabilising the estimates when small samples ($n < 5$) are present (Lai and Ying method – See section 8.1.3).

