## 8. RESEARCH QUESTION AND OBJECTIVES

The study will generate clinical data on the characteristics of adv/mUC patients treated with avelumab and on the effectiveness and safety of avelumab in the real-world setting.

Primary objective: to estimate Overall Survival (OS) of adv/mUC patients treated with avelumab in the real-world setting.

Secondary objectives :

- To describe patients' characteristics: ECOG (0-4) at ChT 1st and avelumab initiation, sex, age, ChT regimens received in 1st line (Cis/Gem, Carbo/Gem, Cis/Carbo/Gem, MVAC regimens, others), median number of ChT cycles received in 1st line, median time between the end of ChT 1st line and the start of avelumab, best response to 1st line chemotherapy (CR, PR, SD; CR-RP, SD), site and histology of the primary tumor (bladder, urethra or upper tract), site of baseline metastasis before ChT and avelumab (visceral vs non visceral), biological abnormalities (neutropenia, lymphopenia, impaired renal function, anemia), PD-L1 status and FGFR abnormality, Bajorin risk classification (0, 1, 2) evaluated before the start of ChT 1st line, use of concomitant

treatments (corticosteroids/anti-inflammatory steroids (AIS)/non-steroidal anti-inflammatory drugs (NSAIDs), angiotensin-II-receptor antagonists (sartans)/angiotensin-converting enzyme (ACE) inhibitors, antibiotics, proton pump inhibitors (PPI)) at avelumab initiation, type of neoadjuvant and adjuvant treatments.

- To estimate: Overall Survival from the start of ChT in 1st line, Progression Free Survival one and two (PFS1 and PFS2). Overall Response Rate (ORR), Duration Of Response (DOR) and Duration Of Treatment (DOT) while receiving avelumab.
- To describe the pattern of progression while receiving avelumab.
- To describe subsequent treatments and response to these treatments.
- To describe the safety profile of avelumab.
- To describe use of premedication (acetaminophen and antihistamine).
- To describe Patient-Reported Outcomes (PROs) related to symptoms via the NCCN/FACT FBISI-18 questionnaire and related to global health via the EQ-5D-5L questionnaire. This objective will be evaluated only among patients initiating avelumab after the start of the study.

The primary and secondary objectives will be evaluated on the overall population and for prespecified subgroups.

- Main subgroup of interest: histology (UC with variant; UC without variant).

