### 9.2.1. Inclusion criteria

Patients must meet all of the following inclusion criteria to be eligible to the study:

1. Patient  $\geq 18$  years of age
2. Patient with locally advanced or metastatic urothelial carcinoma (irrespective of tumor histology) whose disease has not progressed (ongoing stable disease, partial response or complete response) following completion of first-line platinum-based chemotherapy and who has been (retrospective), is (retrospective and prospective), will be (prospective) treated with avelumab.
3. For a patient alive at the moment of the inclusion in the study : the patient must be informed of the study, he/she must be given an information letter signed by the investigator and must not be opposed to the collection of his/her data

For a patient who died before the inclusion in the study : the patient (during his lifetime) must not be opposed in writing to the collection of his data. 4. Patient benefiting from a social security scheme according to local regulations

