1. Patient ≥ 18 years of age
2. Patient with locally advanced or metastatic urothelial carcinoma (irrespective of tumor histology) whose disease has not progressed (ongoing stable disease, partial response, or complete response) following completion of first-line platinum-based chemotherapy and who has been (retrospective), is (retrospective and prospective), will be (prospective) treated with avelumab.
3. For a patient alive at the moment of the inclusion in the study: the patient must be informed of the study, he/she must be given an information letter signed by the investigator and must not be opposed to the collection of his/her data
For a patient who died before the inclusion in the study: the person of trust of the patient must be informed and the patient (during his lifetime) must not be opposed to the collection of his data.
4. Patient benefiting from a social security scheme according to local regulations

Exclusion criteria

5. For a patient alive at the moment of the inclusion in the study: patient without liberty, under tutelage, or unable to give oral consent.
6. Patient enrolled in a prospective interventional clinical trial assessing an investigational product.

Data source:

The data of interest will be reported in an electronic case report forms (eCRF) by the investigator for each included patient, at inclusion and regularly during follow-up, on the basis of the data available in the patients' medical records.

In addition, two questionnaires (ePRO or paper) will be completed by participants who initiated avelumab after the beginning of the study:

PFIZER CONFIDENTIAL

CT24-WI-GL03-RF02 2.0 Non-Interventional Statistical Analysis Plan For Primary Data Collection Study

01-Jun-2020

Page 8 of 28

- *NCCN/FACT FBLSI-18 (Functional Assessment of Cancer Therapy – Bladder Cancer Symptom Inventory) : The FBLSI-18 is a self-administered questionnaire to assess patient bladder cancer-specific symptoms using a ‘core’ set of questions a cancer site-specific bladder subscale. Higher scores indicate a higher degree of bladder symptoms.*
- *EQ-5D-5L (EuroQoL – 5 dimensions 5 level) : The EuroQol EQ-5D-5L is patient-completed generic questionnaire consisting of 2 pages: the EQ-5D descriptive system and the EQ visual analogue scale (EQ VAS) :*

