6 ENDPOINTS AND COVARIATES

6.1 EFFICACY/EFFECTIVENESS ENDPOINT(S)

6.1.1 Time-to-event endpoints

Variable	Role	Data source(s)	Operational definition
Overall Survival (OS)	Time to Event Outcome (primary endpoint)	Patient medical records and CRF	Time (month) from the first injection of avelumab to death, whatever the reason +1
Overall Survival 2	Time to Event Outcome (secondary endpoint)	Patient medical records and CRF	Time (month) from the first injection of the chemotherapy used in 1st line to death, whatever the reason +1
Progression Free Survival (PFS)	Time to Event Outcome (secondary endpoint)	Patient medical records and CRF	Time (month) from the first injection of avelumab to the date of progression or death from any cause +1.
Progression Free Survival (PFS) 2	Time to Event Outcome (secondary endpoint)	Patient medical records and CRF	Time (month) from the first injection of avelumab to the date of progression or death from any cause during the 2nd line of treatment post-avelumab +1.
Objective Response Rate (ORR)	Outcome (secondary endpoint)	Patient medical records and CRF	Proportion of patients with a Complete Response (CR) or Partial Response (PR) as a best response during the avelumab treatment.
Duration Of Response uber avelumab (DOR)	Time to Event Outcome (secondary endpoint)	Patient medical records and CRF	Time (month) from the beginning of the response to progression or death from any cause + 1.
Duration Of	Time to Event	Patient medical	Time (month) from the first to last dose of avelumab + 1.

PFIZER CONFIDENTIAL

CT24-WI-GL03-RF02 2.0 Non-Interventional Statistical Analysis Plan For Primary Data Collection Study

01-Jun-2020

Page 12 of 28

Treatment (DOT)	Exposure	records and CRF	
Patterns of progression under avelumab	Outcome (secondary endpoint)	Patient medical records and CRF	Description of metastatic sites and type of progression (new lesion(s)/progression of known lesion(s)).
OS of subsequent treatment	Time to Event Outcome (secondary endpoint)	Patient medical records and CRF	Time (month) from the first injection of avelumab-subsequent treatment to death, whatever the reason +1

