8.1.3 Analysis of time-to-event data

Kaplan-Meier estimates (product-limit estimates) will be presented together with a summary of associated statistics including the median survival time with 2-sided 95% CIs. In particular, the survival rate at 3, 6, 9, 12, 15, 18 and 24 months will be estimated with corresponding 2-sided 95% CIs. The CIs for the median will be calculated according

PFIZER CONFIDENTIAL

CT24-WI-GL03-RF02 2.0 *Non-Interventional Statistical Analysis Plan For Primary Data Collection Study*

01-Jun-2020

Page 15 of 28

to Brookmeyer and Crowley (Brookmeyer R, 1982) and the CIs for the survival function estimates at the time points defined above will be derived using the log-log transformation according to Kalbfleisch and Prentice (Kalbfleisch JD, 2002) (conftype=loglog default option in SAS Proc LIFETEST) with back transformation to a CI on the untransformed scale. The estimate of the standard error will be computed using Greenwood's formula.

Frequency (number and percentage) of participants with each event type and censoring reasons will be presented.

For each subgroup analysis, comparison of the different modalities to a reference level will be performed using univariate Cox proportional hazard models. Ties will be handled using the Exact option in SAS (Ties=Exact option in SAS PROC PHREG). Results will be expressed in terms of hazard ratios (HR) and a 2-sided 95% CI will be associated to each HR. A HR of 1 equals a lack of association, a HR greater than 1 suggests an increased risk compared to the reference level, and a HR below 1 suggests a decreased risk.

Time of follow-up for each event (OS and PFS)

A Kaplan-Meier estimation for follow-up duration will also be generated to assess the follow-up time reversing the censoring and event indicators.

Handling of left truncation and right censoring:

The overall survival from the first injection of the chemotherapy used in 1st line will cover

a retrospective and/or prospective data collection period. The time to event of interest ("survival" time) or censoring if no event occurs (right censoring) will be based on the 1st line of chemotherapy start date at a time-point preceding the study entry (avelumab start date). As a result, only participants who are still alive are included in the study.

Therefore, the time from 1st line of chemotherapy start date to avelumab start date is called immortal time and corresponds to a left truncation in survival analyses.

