The distribution of an estimator which is both left-truncated and right censored can be estimated using the estimator of Kaplan and Meier (Klein, 1997). The likelihood of conditional survival will be estimated as $S_a(t) = \Pr [X > t \mid X \geq a]$. Occurrence of an event will be studied over time t (the time since the start date) conditional on being free of this event at study entry where a represents the time from the start date to inclusion into the study. This is estimated as follows:

$$\widehat{S}_a(t) = \prod_{a \leq t_i \leq t} \left\{ 1 - \frac{d_i}{Y_i} \right\}, t \geq a$$

where d represents the number of events and Y represents the risk set.

In addition, the Kaplan-Meier estimator does not work well when the size of the risk set is extremely small. This may occur at the end of the curve when right censorings are

PFIZER CONFIDENTIAL

CT24-WI-GL03-RF02 2.0 Non-Interventional Statistical Analysis Plan For Primary Data Collection Study

01-Jun-2020

Page 16 of 28

present and also at the start of the curve if left truncation of data occurs. This latter situation confers early instability in the point estimator of the survival function which may propagate throughout the entire curve. Lai and Ying (Lai, 1991) suggested a solution to this problem by a slight modification of the Kaplan-Meier estimator where events are ignored when the risk set is small:

$$\widehat{S}_a(t) = \prod_{a \leq t_i \leq t} \left\{ 1 - \frac{d_i}{Y_i} I[Y_i \geq cn^a] \right\}, t \geq a$$

where I represents an indicator, n represents the population size and c and a represent constant values. These constant values are used to define a minimum risk set size below which the events are not counted. This minimum risk set size is usually defined in terms of the size n of the study population but for study B9991045, the constants will be set arbitrarily to ensure that the minimum risk set size is equal to 5. The method proposed by Lai and Ying therefore will only be effective for portions of the Kaplan-Meier curve in which the risk set does not exceed 5 participants. This analysis will be performed using the SAS® PROC HPSEVERITY procedure.

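### The left-truncated curve named for OS from chemotherapy start describes neither all chemotherapy starters nor the avelumab-treated patients in the FAS; the SAP should name the OS2 population and add a labelled ordinary Kaplan-Meier.

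*SAP*

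**What the plan says.** OS2 is time "from the first injection of the chemotherapy used in 1st line to death, whatever the reason" (SAP 6.1.1), analysed in the FAS, which contains only enrolled patients who received at least one avelumab injection (SAP 5.1).

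SAP 8.2.2.1 says that survival methods will be used with the same censoring as for primary OS, and then that "a modified Kaplan-Meier estimator will be provided using right censoring and left truncation", stabilised by the Lai-Ying rule when the risk set is small. The summary table in SAP 8.2.5 has one OS 2 row, with plain Kaplan-Meier as the method.

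SAP 8.1.3 gives the reason for truncation. The clock starts before avelumab, and "As a result, only participants who are still alive are included in the study". The estimated quantity is survival "conditional on being free of this event at study entry where a represents the time from the start date to inclusion into the study". The minimum risk set is 5.

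Being alive is not the only entry condition. Protocol 9.2.1, criterion 2, admits patients "whose disease has not progressed (ongoing stable disease, partial response or complete response) following completion of first-line platinum-based chemotherapy". Protocol section 8 describes the study's scope: "The study will generate clinical data on the characteristics of adv/mUC patients treated with avelumab". The OS2 objective itself names no population.

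**The concern.** A delayed-entry Kaplan-Meier needs a target population and an assumption. The assumption is that, at each time since chemotherapy start, patients already under observation have the same death hazard as members of the target who are alive but not yet observed. The SAP states neither.

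Two targets are possible:

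- **All first-line chemotherapy starters.** Living patients who progress on chemotherapy never enter. Those under observation are therefore selected for better prognosis, and the assumption is not credible.
- **Patients who went on to receive avelumab (the FAS).** No member of this group is missing, because surviving to avelumab is part of belonging to it. An ordinary Kaplan-Meier from chemotherapy start describes them. The truncated curve starts to fall as soon as the earliest entrants form a usable risk set. It then applies their post-avelumab hazard to months that the other patients survived by definition.

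The stake is a published secondary estimate that could be low by months for the patients studied, and that does not estimate survival of chemotherapy starters either.

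**Working it through.** **Inputs from the documents.** Exponential OS from avelumab, median 20 months, n = 600 (Protocol 9.5); minimum risk set 5 (SAP 8.1.3); entry at avelumab start (SAP 8.1.3).

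**Assumed inputs.** The distribution of the interval A from chemotherapy start to avelumab start, and, for the simulations, censoring 24 to 48 months after avelumab. The documents give neither.

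**Step 1: the plan's own figure.** Protocol 9.5 gives a 95% CI of [18.6; 21.8] for the median. With the stated mean of 29 months, the median is 29 × ln 2 = 20.10. The exact limits are 20.10 × 1200/χ²(0.975; 1200) = 20.10 × 1200/1297.9 = 18.6 and 20.10 × 1200/1105.9 = 21.8. The figure is reproduced, so the exponential model is the one the plan uses.

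**Step 2: truncated median when A is unrelated to later hazard.** Let λ = ln 2/20 = 0.03466 per month. Every observed risk set has hazard λ, so the curve is exp(−λ(t − a₀)), where a₀ is the time at which the risk set first becomes usable. Its median is a₀ + 20.

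**Step 3: true median in the same patients.** For t beyond the longest interval, P(A + T > t) = exp(−λt) × M, with M = E[exp(λA)]. The median is 20 + ln(M)/λ. For A uniform on (l, u), M = (exp(λu) − exp(λl))/(λ(u − l)).

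| Interval A (months) | M | Truncated median | True median | Gap |
|---|---|---|---|---|
| Uniform 4-6 | 1.189 | 4 + 20 = 24.0 | 20 + 5.0 = 25.0 | 1.0 |
| Uniform 3-8 | 1.212 | 3 + 20 = 23.0 | 20 + 5.5 = 25.5 | 2.5 |
| Uniform 2-10 | 1.235 | 2 + 20 = 22.0 | 20 + 6.1 = 26.1 | 4.1 |
| Gamma, mean 5.5, SD 1.6 | 1.212 | 2.4 + 20 = 22.4 | 20 + 5.5 = 25.5 | 3.1 |

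For the gamma case, shape = (5.5/1.6)² = 11.82, scale = 1.6²/5.5 = 0.465 and M = (1 − 0.465λ)^(−11.82), applied also just beyond the longest intervals as an approximation. Here a₀ ≈ 2.4 is the 5/600 quantile, roughly when the fifth patient enters.

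**Step 4: simulation with censoring and the minimum risk set of 5.** Truncated versus ordinary Kaplan-Meier medians are 24.0 vs 24.9 (uniform 4-6), 23.1 vs 25.4 (uniform 3-8), 22.0 vs 26.0 (uniform 2-10) and 22.4 vs 25.4 (gamma). The ordinary curve recovers the true value and the truncated one does not.

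**Step 5: a reported survival rate.** At 12 months with A uniform 3-8, the truncated curve gives exp(−9λ) = 73%. The true value is exp(−12λ) × 1.212 = 80%.

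**Step 6: interval related to hazard.** If early entrants have the higher hazard (hazard ratio 0.74 per SD of interval), the simulated gaps for the three uniform cases are 1.4, 3.6 and 5.8 months. If later entrants do (1.35 per SD), they are 0.7, 1.8 and 2.9 months. The direction is the same throughout.

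**Step 7: chemotherapy starters, illustration only.** Assume intervals of 3-8 months, 20 to 60% of starters never reaching avelumab, and a median OS of 6 to 12 months for them. The median for all starters is then 11.0 to 22.5 months, while the truncated estimate stays near 23. The documents give none of these inputs; only the upward direction should be taken from this step.

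**The case against.** Delayed entry is a recognised response to immortal time, and the SAP names that problem openly, writes the estimand as conditional on being event-free at entry, and restricts OS2 to the FAS. The ordinary curve contains guaranteed survival and is open to misuse. Which curve should lead is partly a matter of preference. All of this stands, and it is why both curves should be reported rather than one replaced by the other.

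A reader might infer three stronger points that the documents do not support:

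- **That the truncated curve will be the only OS2 output.** It is the only estimator 8.2.2.1 names, but that section also refers to survival methods generally, 8.1.3 promises Kaplan-Meier estimates for time-to-event data, and 8.2.5 lists plain Kaplan-Meier. The text is ambiguous.
- **That the plan presents OS2 as survival of all first-line patients.** No passage says so. The gap is that no OS2 population is named; reading it as the avelumab-treated patients is reasonable but inferred from the FAS and the general study aim.
- **That the error has a known size.** It depends on the spread of the interval, above all on its lower tail, and the documents give no distribution.

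**Conclusion.** The point holds. Because entry requires non-progression, the truncated curve cannot credibly stand for all chemotherapy starters. For the FAS it sits below actual survival from chemotherapy start in every scenario run.

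Under the protocol's exponential model, with the interval unrelated to later hazard, the median is about 1 month too low for intervals of 4 to 6 months and about 2 to 4 months too low for wider ones. Letting hazard depend on the interval widens this to 0.7 to 5.8 months. For scale, the planned 95% CI for the primary median is 3.2 months wide.

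The direction is secure within these scenarios; the size rests on assumed intervals. OS2 is secondary and descriptive, no decision rule depends on it, and primary OS from avelumab is unaffected.

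**What to change.** In SAP 8.2.2.1, with the OS 2 row of 8.2.5 brought into line:

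1. Name the population that OS2 describes.
2. Add the ordinary Kaplan-Meier from chemotherapy start in the FAS. Label it as conditional on reaching avelumab and not for comparison with cohorts counted from chemotherapy start.
3. Report it beside the left-truncated curve. State that curve's independent-entry assumption, and note that inclusion criterion 2 makes it doubtful.

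The cost is a few sentences of SAP text and one extra run, with no new data. The downside is a published curve that contains guaranteed survival, so the label must travel with it into every table and figure.

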8.2.2.2 Progression free survival (PFS)

The PFS will be analyzed using survival analysis method, in the FAS, using the following table for censorship, and date of first study treatment intake as starting date.

Table 2: Event Date and Outcome for PFS

Scenario	Date of Event/Censoring	Outcome
Progression recorded before discontinuation of treatment	Progression date	Event
Death (without any previous recorded progression of treatment)	Death Date	Event
Final discontinuation of treatment during the study before any progression or death	Treatment Discontinuation Date	Censored
Lost to follow-up or early study discontinuation without progression or death	Last News Date	Censored

PFS will also be described by subgroup (See section 5.3 for subgroup definition).

8.2.2.3 Progression Free Survival (PFS) 2

For PFS 2, endpoint will be analyzed using a survival analysis, in the FAS, using the following table for censorship, and date of first study treatment intake as starting date. For this analysis, only participants who initiated a 2nd line post-avelumab systemic treatment will be considered. Local treatments as radiotherapy are not considered as second line post-avelumab.

Table 3: Event Date and Outcome for PFS

Scenario	Date of Event/Censoring	Outcome
Progression recorded during 2 nd line of post-avelumab treatment	Progression date	Event
Death (without any previous recorded progression of treatment) during 2 nd line of post-avelumab treatment	Death Date	Event
Final discontinuation of 2 nd line of post-avelumab treatment during the study before any progression or death	Treatment Discontinuation Date	Censored
Lost to follow-up or early study discontinuation without progression, death or 2 nd line of post-avelumab treatment discontinuation	Last News Date	Censored

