### 9.1.2. Secondary endpoints

- OS from the start of the chemotherapy used in 1st line: time between the first injection of the chemotherapy used in 1st line and the date of death from any cause.
- PFS1: time between the first injection of avelumab and the date of progression or death from any cause. Progression status will be defined according to RECIST 1.1.
- PFS2: time between the first injection of avelumab and the date of progression or death from any cause during the 2nd line of treatment post-avelumab. Progression status will be defined according to RECIST 1.1.
- ORR: proportion of patients with a Complete Response or Partial Response as a best response during the avelumab treatment. Responses to treatment will be defined according to RECIST 1.1.
- DOR: time between the beginning of the response and progression or death from any cause.
- DOT: time between the first and last dose of avelumab.
- Patterns of progression under avelumab: metastatic sites and type of progression (new lesion(s)/progression of known lesion(s)).
- Subsequent treatments and response to these treatments: DOT, PFS, ORR and OS.
- Safety: AEs of any type, grade 3-4 AEs, AEs leading to interruption or discontinuation, AEs leading to death.

090177e1a41aac13\Final\Final On: 28-Jul-2025 13:50 (GMT)

- Premedications (acetaminophen and antihistamine): Proportion of patients who received a premedication at each injection of avelumab. Median number of cycles with premedication. To evaluate the correlation between infusion-related reactions and premedication.
- Evolution of PROs NCCN/FACT FBISI-18 and EQ-5D-5L scores during avelumab treatment.

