8.2.2.5 Duration of response (DOR)

For DOR, endpoint will be analyzed using a survival analysis, in the FAS, using the following table for censorship, and date of first response (Complete Response or Partial Response) as starting date.

Table 4: Event Date and Outcome for DORs

Scenario	Date of Event/Censoring	Outcome
Tumor assessment with a reported progressive disease, after response was observed.	Progression Date	Event
Death (whatever the cause) without treatment discontinuation	Death Date	Event
No reported progressive disease during the study nor death.	Last News Date	Censored
Lost to follow-up or early study discontinuation without stopping treatment	Last News Date	Censored
Treatment discontinuation	Discontinuation Date	Censored

DOR will also be described by subgroup (See section 5.3 for subgroup definition).

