8.2.2.9 PFS of subsequent treatment

For PFS of subsequent treatment, endpoint will be analyzed using survival analysis method, in the FAS for participants receiving at least one dose of subsequent treatment, using the following table for censorship, and date of first intake of subsequent treatment starting date.

Table 6: Event Date and Outcome for PFSs

Scenario	Date of Event/Censoring	Outcome
Progression recorded before discontinuation of subsequent treatment (and after initiation)	Progression date	Event
Death (without any previous recorded progression of disease)	Death Date	Event
Final discontinuation of subsequent treatment during the study before any progression or death	Treatment Discontinuation Date	Censored
Lost to follow-up or early study discontinuation without progression or death	Last News Date	Censored

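### SAP Table 2 censors PFS at avelumab discontinuation although the protocol sets no on-treatment limit, and it gives two outcomes for a patient who stops and later dies

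*SAP*

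**What the plan says.** **Definitions.** Protocol 9.1.2 has "PFS1: time between the first injection of avelumab and the date of progression or death from any cause" and "DOR: time between the beginning of the response and progression or death from any cause". Neither carries an on-treatment limit. SAP 6.1.1 keeps the PFS definition: "from the first injection of avelumab to the date of progression or death from any cause +1".

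**PFS rules (SAP 8.2.2.2, Table 2).**
- Row 1, event: "Progression recorded before discontinuation of treatment".
- Row 2, event at the death date: "Death (without any previous recorded progression of treatment", closed by a bracket and with no condition about being on treatment.
- Row 3, censored at the discontinuation date: "Final discontinuation of treatment during the study before any progression or death".
- Row 4 censors patients lost to follow-up or leaving the study early at the last news date.

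**PFS of subsequent treatment (SAP 8.2.2.9, Table 6).** The structure is the same, with censoring at "Final discontinuation of subsequent treatment during the study before any progression or death". The definition in SAP 6.1.1 again has no such limit.

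**DOR rules (SAP 8.2.2.5, Table 4).** Progression after response is an event, with no condition on discontinuation (row 1). Death counts only as "Death (whatever the cause) without treatment discontinuation" (row 2). Discontinuation is a censoring reason, with no condition that it come before progression (row 5).

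**Related text.** SAP Table 1 (OS) has its own row making death after discontinuation an event. SAP 5.3 defines a long responder as a patient with PFS of at least 12 months, whether or not an event occurred. SAP 8.1.3 tabulates censoring reasons, and SAP 8.2.4 describes stops before progression with their reasons. No analysis that ignores discontinuation is planned.

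**The concern.** There are two separate problems.

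First, the estimand changes without comment. Progression after stopping avelumab is a PFS event under the protocol but not under SAP Table 2. Kaplan-Meier censoring at stopping is valid only if those who stop have the same later risk as those who continue. Patients who stop because they are deteriorating may well not, so the censoring may be informative.

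Second, Table 2 cannot be programmed uniquely. Two programmers could follow it faithfully and produce different PFS curves. This fault needs no assumption about prognosis. It also reaches the subgroups in SAP 5.3, because early progressors and long responders are classified by their PFS value, and those groups are then used for OS, PFS and baseline summaries.

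**Working it through.** **Step 1. Trace example patients through SAP Table 2.**

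| Patient | Protocol 9.1.2 | SAP Table 2 |
|---|---|---|
| A: stops at month 5, dies at month 14, no progression recorded | Event at 14 | Row 2: event at 14. Row 3: censored at 5 |
| B: stops at month 5, progresses at month 7, dies at month 14 | Event at 7 | Censored at 5: row 1 needs progression before stopping, row 2 needs no earlier progression |
| C: stops at month 5, alive without progression at month 20 | Censored at 20 | Row 3: censored at 5 |

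Patient A is a long responder (14 ≥ 12) under row 2 but not under row 3 (5 < 12). Patient C is a long responder by the protocol definition but not by Table 2. The same trace applies to Table 6, with subsequent treatment in place of avelumab.

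**Step 2. Trace SAP Table 4.** A responder who has both a progression and a discontinuation, in either order, meets row 1 (event) and row 5 (censored). A responder who stops and then dies without progression is censored at stopping, whereas Protocol 9.1.2 counts the death.

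**Step 3. Illustrate the size for PFS.** The documents give no PFS figure to reproduce; their only precision figures are for OS. All inputs here are assumptions: on-treatment median PFS 6 months, share q = 20% stopping before progression, exponential times, and a hazard after stopping equal to k = 2 times the on-treatment hazard.

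- On-treatment hazard: h = ln 2 / 6 = 0.1155 per month.
- Stopping hazard: g = h·q/(1−q) = 0.1155 × 0.25 = 0.0289 per month.
- Protocol definition: S(t) = e^(−(h+g)t) + [g/(kh−h−g)]·[e^(−(h+g)t) − e^(−kht)].
- The multiplier is 0.0289/(0.2310 − 0.1155 − 0.0289) = 0.333.
- At 12 months: 0.1768 + 0.333 × (0.1768 − 0.0625) = 0.215.
- At 5.64 months: 0.443 + 0.333 × (0.443 − 0.272) = 0.500, so the median is 5.64 months.
- Row 3 prevailing: the curve follows hazard h alone, so the median is 6.00 months and 12-month PFS is 0.5^(12/6) = 25.0%. The median is 6.00/5.64 = 1.06 times the protocol value.
- Row 2 prevailing: a further assumption is needed, here that 30% of first events after stopping are deaths without recorded progression. Simulation of 400,000 patients gives 5.88 months and 23.8%.

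**Step 4. Vary the assumptions.** The simulation used on-treatment medians of 4, 6 and 9 months, with 10% to 30% stopping first. It compares the row 3 median with the protocol median.

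| Hazard after stopping | Difference in median |
|---|---|
| Halved | −2% to −8% |
| Unchanged | 0% |
| 2 to 4 times | +3% to +22% |

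**The case against.** **Severity.** These are secondary endpoints in a study with no hypotheses and purely descriptive analyses (SAP 4.1 and 4.2). Primary OS counts deaths after discontinuation. Censoring reasons and early stops are reported, so a reader would see how many patients are affected. This stands as a reason not to rank the point higher. It does not settle which row of Table 2 applies.

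**Direction.** A reader might infer that PFS and DOR are necessarily overstated, or that patients leave the risk set just before they progress. The documents do not support this. They give no rate, timing or prognosis of stopping, and Step 4 shows that the bias can be nil or reversed. Nor can one say that a fixed share of events is discarded: that share would only restate the assumed stopping fraction, and it depends on which row prevails.

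**Comparison with the randomised trial.** A reader might also infer that results could not be set beside JAVELIN Bladder 100. That would need the trial's PFS censoring rules. The documents quote only its OS results.

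**DOR.** The objective in Protocol section 8 ties response rate, DOR and treatment duration to time on avelumab, and SAP 6.1.1 labels DOR in the same way. This gives partial support to an on-treatment DOR, so the protocol is mixed on that endpoint. PFS has no such support.

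**Data capture.** The protocol's data-collection table (section 9.3) lists repeated tumour evaluations under response on avelumab. After stopping, it lists progression only under subsequent treatments. Progression in the interval between the two may be missed, in which case an event would be dated late. This objection stands and belongs in the remedy.

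**Conclusion.** The point holds for PFS. SAP Table 2 departs from both the protocol definition and the SAP's own, and it assigns two outcomes to a patient who stops and later dies without recorded progression. Table 6 has the same rule and the same overlap, contrary to the definition in SAP 6.1.1; Protocol 9.1.2 names PFS of subsequent treatment without defining it. Table 4 overlaps in a different way, and its on-treatment limit must be reconciled with Protocol 9.1.2 and section 8.

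Informative censoring is a risk, not a demonstrated fact. Under the assumed inputs of Step 3, Table 2 lengthens the median by about 0.4 months if row 3 prevails (6.00 − 5.64) and by about 0.2 months if row 2 prevails (5.88 − 5.64). Step 4 shows how far this depends on the hazard after stopping. The overall primary OS estimate is unaffected, although OS by early-progressor and long-responder status inherits the ambiguity. This should be fixed before analysis, but it does not threaten the study's main result.

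**What to change.** - **SAP Table 2:** make the first recorded progression or death an event whether it falls before or after discontinuation, and delete the discontinuation-censoring row. Widen the last row so that it covers every patient without a recorded event, including those who stopped and remain event-free.
- **Sensitivity analysis:** keep the discontinuation-censored version, labelled as such, and state how a death after stopping is handled in it.
- **SAP Table 6:** align it with the definition in SAP 6.1.1, and state whether a progression first recorded on a later line counts.
- **SAP Table 4:** either make the same change or state explicitly that DOR is on-treatment and reconcile that with Protocol 9.1.2. In both cases add a precedence rule so that progression before discontinuation is always an event.
- **SAP Table 3:** leave unchanged. The protocol itself limits PFS2 to events during the second line after avelumab.
- **SAP 5.3:** state that the early-progressor and long-responder groups use the revised PFS.

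The cost is SAP table edits and programming. Protocol 9.1 already collects clinical data every three months to death or study end, so deaths after stopping should be available. The downside is that progression between stopping avelumab and the next treatment may be incompletely recorded. The sponsor should confirm that it is captured and report its completeness beside the sensitivity analysis.
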